diastole. Volumes will be measured using Simpson's rule. Stroke volume will be calculated by subtracting EDV from ESV. Q will be calculated as HR multiplied by SV. Three beats will be measured and the average will be used in the analyses. Ejection fraction (EF) will be calculated from the ventricular volumes and expressed as a percentage of ESV to EDV. Mitral valve velocities will be obtained from the apical 4 chamber view, whereby E, A, and E/A will be measured. The slope of the inflow will also be determined. Tissue Doppler will also be performed to obtain E' with E/E' calculated. Lastly, speckle tracking will be performed using Aloka's tissue tracking software.

Maximal Oxygen Consumption (VO₂peak)

Cardiorespiratory fitness (VO₂peak) will be measured using an incremental exercise test on a motorized treadmill following a Modified Balke protocol while analyzing expired gases (TrueOne, Parvo Medics, Sandy, UT) to determine maximal oxygen consumption. Due to differing fitness levels by design, participants will choose a comfortable walking/jogging pace to perform a 5-minute warm-up at 0% incline. The work rate will increase by 2.5% grade every 2 minutes up to 12.5%, after which speed will increase 0.5 mph/minute with constant grade until exhaustion. VO₂peak (ml·kg⁻¹·min⁻¹) will be based on highest recorded 20-second VO₂ value when two of three criteria are satisfied: 1) respiratory exchange ratio ≥ 1.10 ; 2) peak heart rate within 10 bpm of age-predicted maximum; or 3) peak rating of perceived exertion ≥ 17 . Heart rate, blood pressure, and oxygen uptake will be monitored throughout the exercise and recovery.

For Specimen Collection Studies

Blood samples (15 ml each; 30 ml Visit 1, 15 ml Visit 2, 30 ml Visit 3) will be collected from participants following standard procedures. All study personnel collecting blood samples have been trained by UIC's CCTS/CRC staff. The samples will be analyzed for C-reactive protein and interleukin-6 for inflammatory markers, oxidized LDL as a marker of oxidative stress, and total antioxidant capacity and ascorbate for antioxidant capacity (in which additional analyses on inflammatory markers may be performed) following the specified ELISA procedures. Samples will be stored separate from the study data and be de-identified. The samples will be kept indefinitely for future analysis if specific consent is provided by participants. If consent is not provided, samples will be properly destroyed following study completion.

Studies involving use of product

Participants will receive a Typhoid Vi Polysaccharide Vaccine (Typhim Vi, Sanofi Pasteur SA). It will be administered intramuscularly at the deltoid (upper arm) of the non-dominant arm in a dose of 0.5 mL by a registered nurse. The product will be purchased from the manufacturer through UIC Investigational Pharmacy. The vaccination will be stored at 35° to 46° F in a temperature controlled refrigerator

in the Integrative Physiology Lab in the DHSP Building in a locked room in a controlled access suite. On-study personnel will have access. A log will be kept with date and subject number for each dose of the vaccine used. Adverse events will be immediately reported to the principal investigator, who will complete an Adverse Event Report Form. If it is deemed a severe adverse event, it will be reported to the IRB within 24 to 48 hours. Based on data from clinical trials with over 4,000 subjects, adverse reactions may consist of: local tenderness, pain, induration or erythema at the injection site; or, a systemic response of malaise, headache, myalgia, nausea, diarrhea, feverish, or vomiting. No severe or unusual side effects were observed and most adverse experiences were generally limited to 48 hours.

Participants will also receive 2g Vitamin C on the first and third visit. It will be administered orally. Supplementation will be ingested in front of laboratory personnel. This supplementation does not exceed daily recommendation and has been previously shown to acutely improve endothelial function[35–39]. The product will be purchased and stored in the IPL in the DHSP Building. On-study personnel will have access. A log will be kept with the date and subject number for each dose given. Adverse events will be immediately reported to the principal investigator, who will complete an Adverse Event Report Form. If it is deemed a severe adverse event, it will be reported to the IRB within 24 to 48 hours. There are no known risks associated with the administration of Vitamin C. The dosage of antioxidant vitamins are the same as those sold over the counter and safe. No side effects have been reported with this dose.

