For central blood pressure, radial artery pressure waveforms will be attained in the supine position from a 10-second epoch using applanation tonometry and a high-fidelity strain gauge transducer (Millar Instruments, Houston, TX) [43]. A central aortic pressure waveform is reconstructed from the aforementioned radial artery pressure waveform using a generalized validated transfer function (SphygmoCor, AtCor Medical, Sydney, Australia). From this reconstructed waveform, aortic pressures, end-systolic pressure, and sub-endocardial viability index (a ratio of diastolic to systolic pressure-time intervals) will be obtained [43]. Only recordings receiving an in-device quality index $\geq 80\%$ will be included in analysis [43]. This index is derived from a weighted algorithm that examines average pulse height (average height of the pulse waveforms measured), pulse height variation (amount of variation in the height of the pulse waveforms measured), and the diastolic variation (an index of baseline pressure consistency during the measurement attained from the variation in the diastolic inflection point of the pulse waveform). Previous work shows that reproducibility of measures attained from this technique is high [44].

Pulse wave velocity (PWV)

Approximately 20-sec of pressure waveforms will be collected at the brachial, common carotid, and femoral arteries using a high-fidelity strain-gauge transducer. PWV will be calculated from the distances between measurement points and the measured time delay between proximal (carotid) and distal (femoral) waveforms (NIHem, Cardiovascular Engineering Inc.). The brachial waveforms will not be used for PWV calculations, but are necessary for calibrating carotid blood pressure (described below).

Carotid Blood Pressure

Carotid artery pressure waveforms obtained during the measurement of PWV will be ensemble averaged to construct a carotid pressure waveform. This carotid waveform is then calibrated to brachial waveforms and brachial mean and diastolic pressure. The resulting carotid systolic pressure is necessary for calibrating carotid stiffness measures (described below).

Flow-Mediated Dilation (FMD)

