Cerebral blood flow velocity will be measured for 7 minutes in a resting state in the middle cerebral artery (MCA) using two 2-MHz transcranial Doppler ultrasound probe (TOCM Neurovision, MultiGon Industries, INC. Elmsford NY) fitted with a specific cushioned headpiece to hold the probe in place. The Doppler probe will be placed at the temporal window on the side of the head to insonate the vessels. The blood velocity wave form will be recorded continuously at 500 Hz and stored off-line for subsequent analysis of the systolic, diastolic and mean blood flow velocities. Brain blood velocity is influenced by carbon dioxide, thus, we will monitor end tidal CO₂ throughout this testing period. A 5-minute average at the end of the 7 minute period will be used for analyses.

Carotid Ultrasonography

Carotid stiffness:

Carotid stiffness is a common clinical marker and independent risk factor for future vascular events. Carotid stiffness will be assessed using high fidelity ultrasound (Hitachi Aloka Alpha 7, Japan) and high frequency (7-13 MHz) linear probe. Carotid artery distension will be assessed using wall-tracking and simultaneous measurement of blood velocity. Stiffness measures are generally calculated by adjusting carotid artery compliance for changes in carotid blood pressure. Measures of carotid stiffness will include carotid B-stiffness, Elastic modulus, and PWV-B using the following equations:

$$\text{B-stiffness} = (\log P_1/P_0)/(D_1-D_0)/D_0;$$

$$\text{Elastic modulus} = (P_1/P_0)/((D_1-D_0)/D_0)$$

$$PWV-B = (\sqrt{((B\text{-stiffness}) \times P_1) / 2\rho}) / 2\rho$$

where P_1 and P_0 are the highest (systolic) and lowest (diastolic) carotid pressures and D_1 and D_0 are the maximum (systolic) and minimum (diastolic) diameters.

Carotid Blood Flow:

Carotid blood flow will be measured on the neck using the same ultrasound probe described for carotid stiffness. Carotid artery diameter and blood velocity will be measured with the probe placed on the skin over the carotid artery with 60 degree insonation angle. Common carotid blood flow will be assessed approximately 1-2 cm proximal to the carotid bifurcation. Internal carotid blood flow will be measured just distal to the carotid bifurcation to obtain measures of carotid blood flow that feed directly into the middle cerebral arteries.

Cognitive Function

Montreal Cognitive Assessment (MOCA):

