12.0 Statistical Considerations

The data will initially be examined for normality violations, entry errors, and missing values. Entry errors will be corrected by double-checking with original data files. Non-normally distributed data will have an appropriate transformation applied to achieve normality (i.e. log transformation, square root, etc.).

All analyses will be adjusted for age, sex, and body mass index, which are all factors known to influence hemodynamic parameters. Additionally, due to multiple tests, a correction will be applied for multiple comparisons (α divided by the number of tests). Significance level will be set at $\alpha=0.05$, with a Bonferroni correction used to correct for multiple comparisons.

Aim 1: The effects of acute inflammation on endothelial and microvascular function will be tested with a two-way group (3) by time (2) repeated measures ANOVA (V2 and V3 baseline). We expect older high fit adults to have similar vascular reactivity as young adults, i.e. decreased FMD and NIRS reperfusion, suggesting that fitness maintains vascular reactivity during an inflammatory insult with age. If no difference in the response to acute inflammation is seen between low and high fit older adults (not expected), this would indicate fitness is not protective with age during acute inflammation.

Aim 2: The effects of ascorbic acid ingestion will be tested with a two-way group (3) by time (2) repeated measures ANOVA to determine if the antioxidant caused changes at Visit 1 (baseline) or Visit 3 (acute inflammation). A two-way group (3) and time (3) repeated measures (V2 baseline, V3 before and after Vit C) ANOVA will determine if the antioxidant attenuated endothelial function during acute inflammation. At baseline, we expect ascorbic acid to improve vascular function, i.e. increase FMD and NIRS reperfusion, in older low fit adults, with no changes seen in young or high fit older adults. During acute inflammation, we expect ascorbic acid to restore vascular function to baseline in young and older high fit adults. If ascorbic acid does not alter vascular function during acute inflammation, this would indicate another mechanism other than oxidative stress is contributing to vascular dysfunction.

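### The carotid elastic modulus is printed as a pressure ratio over strain, and the B-stiffness and PWV-B equations also fail as printed

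*Combined protocol and SAP*

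**What the plan says.** Section 6.0, under Carotid Ultrasonography, commits to explicit formulas: "Measures of carotid stiffness will include carotid B-stiffness, Elastic modulus, and PWV-B using the following equations". In plain notation the three lines are:

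- B-stiffness = (log P1/P0)/(D1−D0)/D0
- Elastic modulus = (P1/P0)/((D1−D0)/D0), printed as "Elastic modulus} = (P_1/P_0)/((D_1-D_0)/D_0" plus a closing bracket
- PWV-B = sqrt((B-stiffness × P1)/2ρ)/2ρ

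The legend defines the pressures ("where P_1 and P_0 are the highest (systolic) and lowest (diastolic) carotid pressures") and the diameters ("D_1 and D_0 are the maximum (systolic) and minimum (diastolic) diameters"). It does not define ρ, the base of the logarithm or any unit. The Carotid Blood Pressure paragraph explains where the pressure comes from: "The resulting carotid systolic pressure is necessary for calibrating carotid stiffness measures". No other section restates the equations or says that device software will supply the indices instead.

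Section 12.0 describes the Aim 1 analysis thus: "The effects of acute inflammation on endothelial and microvascular function will be tested". Its stated expectations for both aims are in terms of FMD and NIRS reperfusion. Carotid stiffness is not named there.

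**The concern.** An elastic modulus is stress over strain and must carry a pressure unit. The printed one carries none, so it cannot be what its name says. The same section explains that stiffness measures adjust compliance for changes in carotid pressure, yet a ratio P1/P0 cannot register a proportional rise in both pressures.

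The other two lines fail a check against each other. The root in PWV-B gives a velocity only if B-stiffness is unitless. As printed, without a bracket round the strain, B-stiffness has units of 1/length². The second division by 2ρ then breaks the units of PWV-B whichever B-stiffness is used.

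The modulus and B-stiffness errors are not constant rescalings, so they would not simply drop out of comparisons between groups or visits if someone programmed the equations as they stand.

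**Working it through.** The documents give no stiffness value to reproduce, so this is a dimensional check plus direct evaluation.

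**Inputs.** The formulas and the definitions of P and D are from section 6.0. Assumed, because the documents give no figures: base case 120/80 mmHg, D0 = 6.0 mm, D1 = 6.5 mm (strain 0.5/6.0 = 0.0833), ρ = 1050 kg/m³, natural log. The range tried was 110/70 to 140/80 mmHg with strain of about 4% to 10%.

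**1. Elastic modulus.** Printed form: (120/80)/0.0833 = 18.0, no unit. Pressure-difference form: 40/0.0833 = 480 mmHg = 64.0 kPa. At the same strain:

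| Pressure (mmHg) | Printed form | (P1−P0)/strain |
|---|---|---|
| 90/60 | 18.0 | 48 kPa |
| 120/80 | 18.0 | 64 kPa |
| 150/100 | 18.0 | 80 kPa |

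With almost no pulse pressure the ratio is about 1 and the printed form still gives 1/0.0833 = 12.0, where a modulus should tend to zero.

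It can also move when the modulus has not. Take 120/75 mmHg at strain 0.0833, then 135/75 mmHg at strain 0.1111, so that pulse pressure rises from 45 to 60 mmHg with strain in proportion. The pressure-difference form is 45/0.0833 = 60/0.1111 = 540 mmHg both times. The printed form goes from 1.6/0.0833 = 19.2 to 1.8/0.1111 = 16.2, a fall of 15.6%.

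**2. B-stiffness.** Bracketed form: ln(1.5)/0.0833 = 0.4055/0.0833 = 4.87. Printed form, read left to right: 0.4055/0.5/6.0 = 0.135 per mm². The second is the first divided by D0² (4.87/36 = 0.135). With 120/80 mmHg and a fixed 8% strain:

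| D0 (mm) | Bracketed | Printed (per mm²) |
|---|---|---|
| 5 | 5.07 | 0.203 |
| 6 | 5.07 | 0.141 |
| 7 | 5.07 | 0.103 |
| 8 | 5.07 | 0.079 |

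At equal beta, 7 mm against 6 mm gives (6/7)² = 0.735, which is 27% lower. Within one person over 24 hours the distortion comes only from a change in D0: an assumed 1% change shifts the index by about 2%. This is therefore mainly a between-group matter.

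**3. PWV-B.** 120 mmHg is 15,999 Pa. With bracketed B-stiffness and one 2ρ: sqrt(4.87 × 15,999/2100) = 6.1 m/s. The outer division is by 2 × 1050 = 2100, which leaves 0.0029 and divides a velocity by a density. If printed B-stiffness were fed in, PWV-B would also inherit a 1/D0 dependence: 6/7 = 0.857, or 14% lower at 7 mm than at 6 mm.

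**Range.** Over the assumed inputs (ρ 1050 to 1060) the repaired forms give B-stiffness 4.5 to 13.1, modulus 53 to 187 kPa and PWV-B 5.6 to 10.8 m/s.

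**The case against.** **Conversion faults.** A bracket can be lost, or a stacked fraction flattened into a repeated term, when a PDF is converted to text. For B-stiffness and PWV-B this stands, and the original must be consulted before either line is called the authors' error. It is a weak defence of the modulus, where the minus signs in D1−D0 survive on the same line. Plain prose nearby also shows formula slips: the Heart function paragraph takes stroke volume as ESV minus EDV and bases ejection fraction on ESV over EDV.

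**Notation.** The modulus line brackets the same strain correctly, so the intended B-stiffness is recoverable. The logarithm is under-bracketed too and is readily understood as log(P1/P0). This also stands: the size effect arises only if the literal string is computed.

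**Peripheral measure.** Carotid stiffness has no row of its own in the section 6.0 timetable and is not named in the section 3.0 aims or the section 12.0 analyses. Carotid-femoral PWV comes from distance and time delay. Section 9.0 calls the study hypothesis generating. All of this limits the weight of the point, but none of it makes the printed equations usable.

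**Stronger readings.** A reader might infer that the plan as written yields a PWV-B of about 0.003 m/s. That figure needs SI units, an assumed ρ and a B-stiffness already repaired. Taken wholly as printed in the base case, the number is about 0.0005, 0.0048 or 0.48 with diameters in mm, cm or m, and it is not in m/s in any unit system. A reader might also infer that the study's stiffness results, or its main comparisons, are biased. Nothing shows that the laboratory computed from these lines, and the documents give no evidence that carotid diameters differ between the groups.

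**Conclusion.** The point holds, with limited weight. The modulus line is wrong as printed: it has no pressure unit, does not respond to a proportional rise in both pressures at fixed strain, and in one assumed example falls about 16% while pulse pressure over strain is constant. B-stiffness and PWV-B also fail as printed, subject to checking the original PDF. The literal B-stiffness carries a 1/D0² dependence on artery size. The literal PWV-B is shrunk about 2100-fold in SI units and is not a velocity.

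The dimensional findings need no assumption beyond the printed text. The sizes rest on assumed pressures, diameters and ρ. Whether any study value is affected depends on whether these forms were ever used in calculation, which the documents do not say.

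**What to change.** Check the B-stiffness and PWV-B lines against the original PDF, then restate all three in section 6.0 with full brackets:

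- beta = ln(P1/P0)/((D1−D0)/D0)
- elastic modulus = (P1−P0)/((D1−D0)/D0)
- PWV-B = sqrt(beta × P1/(2ρ))

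Keep P1 in PWV-B, as the document has it, unless the investigators specify another pressure. The choice matters: in the base case P1 gives 6.1 m/s and P0 gives 5.0 m/s. Define ρ and its value, the log base, and the pressure and diameter units. Alternatively, state that the device software computes the indices and drop the equations.

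Check whether any values were calculated from the printed forms. If so, recompute them from the stored pressures and diameters. The cost is a wording correction and a check of the calculation sheet; no new data are needed.

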A blood sample will be collected at baseline during each visit (3 times) and following Vit C consumption (2 times). During the first visit, each blood sample will be 15 mL (approximately 1 tbsp). On visit 2 and 3, the baseline blood draw will be 25 mL (approximately 5 tsp). The final blood draw on visit 3 will be 15 mL (approximately 1 tbsp). At all time points, we will measure C-reactive protein and interleukin-6 for inflammatory markers, oxidized LDL as a marker of oxidative stress, total antioxidant capacity and ascorbate for antioxidant capacity, and endothelial extracellular vesicles, in which additional analyses on inflammatory markers may be performed. The baseline blood draw of visit 2 and 3 will also assess the cholesterol panel (Total cholesterol, HDL cholesterol, non-HDL cholesterol, triglycerides, LDL cholesterol, TC/HDL ratio) and glucose. The additional 10 mL during the baseline blood draw on visit 2 and 3 will be used for analyses of peripheral blood mononuclear cells, which provide valuable information about immune function. Immediately after acquisition of venous blood, plasma or serum will be separated by centrifugation (3000g at 4°C for 15 minutes), placed in aliquots, and stored at -80°C.

Blood pressure

Blood pressure will be measured in the arm using an automated microprocessor controlled ambulatory blood pressure monitor (Mobil-O-Graph 24 PWA, I.E.M, Stolberg Germany) in the supine position according to the guidelines of the American Heart Association. BP will be measured twice, one minute apart, and the average of the two values will use as resting BP. If the two BP measurements

differ by more than 5 mmHg, a third measurement will be taken. Cardiovascular variables such as derived ascending aortic BP waveform and central arterial indices (PWV and pulse wave analysis), stroke volume and cardiac output can be calculated from the pressure waveforms.

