The MOCA is a tool that can be used to systematically and thoroughly assess global cognitive status. It assesses different cognitive domains: attention and concentration, executive functions, memory, language, visuoconstructional skills, conceptual thinking, calculations, and orientation. The maximum score is 30, in which a score of 26 or greater is considered normal. The MOCA takes only 8-12 minutes to administer and is therefore practical to use repeatedly and routinely.

Symbol Digits Modality Test (SDMT):

The SDMT is a global test of cognitive impairment and is associated with selective attention and working memory. This test involves a visual substitution task, whereby the individual has 90 seconds to orally pair specific numbers with given geometric figures as quickly as possible. The test score is the number of correctly paired shapes/numbers.

N-back:

The N-back is a working memory task that lasts approximately 8 minutes.

Participants will be presented with a series of digits one at a time. They will be instructed to press the 'right' response button if the number presented to them matches the digit that was presented 2 numbers previously. Participants will be instructed to hit the 'left' response button for every digit presented to them that does not match the number 2 digits prior. This test is widely used in cognitive psychology as a measure working memory and has been used previously following acute perturbations.

Heart function (cardiac echocardiography)

Cardiac output (Q), stroke volume (SV), and end systolic volume (ESV) will be assessed at rest using two-dimensional echocardiography via a Hitachi Aloka Alpha 7 system (Tokyo, Japan). With subjects in the left lateral position, measurements will be obtained using the four-chamber apical view. The interior of the left ventricle will be traced manually during both end systole and end

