10.0 Quality Control and Quality Assurance

All raw data will be checked by [name], as it is collected and all procedures of the protocol will be performed by trained personnel. Biweekly examination of the analyzed data will be performed by [name] to ensure high quality analysis is being performed.

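### The echocardiography text in Section 6.0 defines stroke volume with the wrong sign and ejection fraction as its complement (minor wording correction)

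*Combined protocol and SAP*

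**What the plan says.** The text is the heart function (cardiac echocardiography) paragraph under Measurements in Section 6.0 of the combined protocol and SAP. It opens: "Cardiac output (Q), stroke volume (SV), and end systolic volume (ESV) will be assessed at rest". On acquisition it says: "The interior of the left ventricle will be traced manually during both end systole and end" diastole, with volumes obtained by Simpson's rule. Three derivation rules follow:

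- Stroke volume: "Stroke volume will be calculated by subtracting EDV from ESV".
- Cardiac output: "Q will be calculated as HR multiplied by SV".
- Ejection fraction: derived from the ventricular volumes and "expressed as a percentage of ESV to EDV".

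No other section gives a different formula. Section 6.0 schedules heart function at Visit 2, before the vaccine, and again at Visit 3, 24 hours later. The aims in Section 3.0 and the tests named in Section 12.0 concern endothelial, microvascular and vascular function. Cardiac measures appear in neither.

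**The concern.** The paragraph is a measurement rule, and anyone deriving the echo variables would turn to it. Two of its three rules are wrong as written, and the third (cardiac output) carries one of those errors forward.

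Heart function is recorded before and after the inflammatory stimulus, so the natural summary is a signed change from Visit 2 to Visit 3. Under the literal rules that change has the wrong direction for stroke volume, cardiac output and ejection fraction, and ejection fraction also has the wrong level. The ejection fraction error is the harder one to see. A negative stroke volume is impossible on its face, whereas ESV/EDV is a positive percentage of ordinary appearance.

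**Working it through.** **Inputs.** The formulas come from the heart function paragraph. EDV is not spelled out there and is read as end-diastolic volume. The documents give no volumes or heart rates, so those below are assumptions. There is no stated figure to reproduce.

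**Formulas.**

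- As written: SV = ESV − EDV; Q = HR × SV; EF = 100 × ESV/EDV.
- Correct: SV = EDV − ESV; Q = HR × SV; EF = 100 × (EDV − ESV)/EDV.

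Hence as-written SV = −(correct SV), as-written Q = −(correct Q), and as-written EF = 100 − correct EF, because ESV/EDV = 1 − (EDV − ESV)/EDV. These are identities and do not depend on the assumed volumes.

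**Levels** (volumes in mL, Q in L/min, EF in %; each pair is as written / correct).

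| EDV | ESV | HR | SV | Q | EF |
|---|---|---|---|---|---|
| 100 | 35 | 60 | −65 / +65 | −3.9 / +3.9 | 35.0 / 65.0 |
| 120 | 50 | 60 | −70 / +70 | −4.2 / +4.2 | 41.7 / 58.3 |
| 120 | 40 | 70 | −80 / +80 | −5.6 / +5.6 | 33.3 / 66.7 |
| 150 | 60 | 60 | −90 / +90 | −5.4 / +5.4 | 40.0 / 60.0 |
| 90 | 45 | 70 | −45 / +45 | −3.15 / +3.15 | 50.0 / 50.0 |

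For the second row: 50 − 120 = −70; −70 × 60/1000 = −4.2; 100 × 50/120 = 41.7; 100 × 70/120 = 58.3. The two ejection fractions coincide only at 50%.

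**Direction of change.** Suppose ESV rises from 50 to 56 mL at Visit 3, with EDV at 120 mL and heart rate at 60.

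- SV: correct 70 to 64, a change of −6 mL; as written −70 to −64, a change of +6 mL.
- Q: correct 4.20 to 3.84, a change of −0.36 L/min; as written +0.36 L/min.
- EF: correct 58.3% to 53.3%, a change of −5.0 points; as written 41.7% to 46.7%, a change of +5.0 points.

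The magnitude of the as-written SV still falls (70 to 64), so a reader who ignored the minus sign would read SV and Q correctly. EF offers no such cue.

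**Effect on tests.** Each as-written measure is a constant (0 or 100) minus the correct one, so every participant's change score is multiplied by −1. Mean changes and coefficients for change reverse sign, while sums of squares are unchanged. An untransformed group-by-time F statistic and its p-value are therefore identical under both definitions, with or without covariate adjustment.

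The equality need not survive the transformations that Section 12.0 allows for non-normal data. Logs and square roots of negative SV and Q do not exist. For EF in the example above, the log change is ln(64/70) = −0.090 under the correct rule and ln(56/50) = +0.113 as written, which are not mirror images.

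**The case against.** The strongest reply is that this is a proofreading matter. Nothing in the documents shows that any calculation follows the wording. Both volumes are traced, so no information is lost. Section 10.0 provides for checks of raw and analysed data, and Section 12.0 adds: "The data will initially be examined for normality violations, entry errors, and missing values". Uniformly negative stroke volumes would not survive those checks. No aim or named test uses the cardiac measures, and Section 9.0 calls the study hypothesis generating.

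All of that stands, and it sets the severity. It does not make the text right, and it covers ejection fraction less well. The inverted value can be caught inside the data set, since 70/120 = 58.3% contradicts 41.7%, but the documents plan no such comparison.

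A reader might infer more than the documents support:

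- *That EDV is not measured, because the opening sentence omits it.* That sentence is not an exhaustive list: it also leaves out ejection fraction, E/A and E'. The ventricle is traced at end diastole, and EDV is named in the formulas.
- *That the blood pressure subsection supplies an independent check.* It says only that "stroke volume and cardiac output can be calculated from the pressure waveforms". It does not commit to calculating them or to comparing them with the echo values.
- *That the follow-up letters in Section 8.0 would be misdirected.* That section provides for a letter if echocardiogram abnormalities are found, but it gives no ejection fraction criterion.

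**Conclusion.** The point holds as a minor definition error. Read plainly, the stroke volume rule gives a negative value for every ejecting ventricle, cardiac output follows it, and the ejection fraction rule gives 100% minus the true value. That conclusion is algebraic; only the illustrative sizes rest on assumed volumes and heart rates. Harm arises only if the text is applied literally, and the realistic route is a wrongly reported level or direction of change in ejection fraction.

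It would be wrong to infer that the planned results are compromised. The endothelial and microvascular analyses and the sample size are untouched, and untransformed group-by-time tests on cardiac measures would give the same F and p. A wording slip is the most likely explanation.

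**What to change.** Correct two statements in the heart function paragraph of Section 6.0:

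- SV = EDV − ESV.
- EF = 100 × (EDV − ESV)/EDV.

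The cardiac output rule can stand, since it is right once stroke volume is right. Then confirm that the calculations actually used for the echo variables follow these definitions. If any values were derived literally, they can be converted without re-tracing: reverse the sign of SV and Q, and replace EF by 100 − EF.

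The cost is two edited statements and one check of the derivations. Data collection does not change, and there is no downside.
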